Because this project has been discontinued for this year, we are paying enrolled participants for completing the baseline assessment. We've been asked by the school principal to pay students who have finished the first survey since they will not go through the intervention or have the opportunity to take future surveys, and therefore receive compensation. The amount would be a \$20 online gift card, which is what they would be paid for the first follow-up assessment.

4.5 Non-monetary compensation. Describe any non-monetary compensation that will be provided. Example: extra credit for students; a toy for a child. If class credit will be offered to students, there must be an alternate way for the students to earn the extra credit without participating in the research.

All youth in the class will receive project t-shirts, culturally relevant study posters, pens, writing pads, and water bottles for participation.

4.6 Will data or specimens be accessed or obtained for recruiting and screening procedures prior to enrollment?

Examples: names and contact information; the information gathered from records that were screened; results of screening questionnaires or screening blood tests; Protected Health Information (PHI) from screening medical records to identify possible subjects.

→ If no, skip the rest of this section; go to [question 5.1](#).

→ If yes, describe the data and/or specimens (including PHI) and whether it will be retained as part of the study data.

4.7 Consent for recruiting and screening. Will consent be obtained for any of the recruiting and screening procedures? ([Section 8: Consent of Adults](#) asks about consent for the main study procedures).

"Consent" includes: consent from individuals for their own participation; parental permission; assent from children; consent from a legally authorized representative for adult individuals who are unable to provide consent.

Examples:

- For a study in which names and contact information will be obtained from a registry: the registry should have consent from the registry participants to release their names and contact information to researchers.
- For a study in which possible subjects are identified by screening records: there will be no consent process.
- For a study in which individuals respond to an announcement and call into a study phone line: the study team person talking to the individual may obtain non-written consent to ask eligibility questions over the phone.

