These examples are of the most sensitive and risky questions we may ask. None of the measures are intended to capture information on suicidality or some other condition that would need referral or notification to some other entity. Please note the follow-up assessment are about 10 minutes shorter as we will not be collecting any lifetime behaviors questions.

Alcohol, Tobacco and Other Drug Use.

Current alcohol use. Participants will be asked if they drank alcohol in the past 30 days

Problem drinking, GAINS Short Screener for youth

ATOD Age initiation. Age of first alcohol, tobacco, marijuana and other drug use.

Peer Alcohol Associations. Number of friends that drink often, peer encouragement to drink or get drunk.⁴²

Susceptibility to initiate ATOD among self-reported non-smokers, non-drinkers, and non-drug users we will ask 6 questions on a 4-point scale: (eg. "if one of your best friends offered you a cigarette/joint/drink, would you smoke it?").

Specific Event Drug and Alcohol Refusal Efficacy scale (SEDARE) perceived likelihood that youth will use drugs and alcohol in specific situations and inquires whether the respondent would be tempted to use alcohol or marijuana in eight potentially stressful or pressured situations.⁴³

Non-ceremonial tobacco use. Adapted from the NSDUH include current cigarette use, vaping and juuling.

Adolescent Sexual and Reproductive Health.

Sexual activity. Adolescent Sexual Risk Behavior 11-item and Adolescent Sexual Activity Index (ASAI) 10 items assess current and past sexual practices with most items focused on pre-coital behaviors during last 12 months for the sexual activities with other youth. If yes to pre-coital behaviors additional items assess if they have engaged in sexual intercourse, frequency, frequency of sex without birth control, frequency of sex without a condom; number of different sexual partners; and whether or not alcohol or drugs were used at first sex experience and/or last time had sex.

Safer sex intentions. Health Belief Model-Intentions for Safer Sex (HBMI) 7-item/5 pt scale (e.g., "I do not plan on having sex until I am at least 18 years old").

Predictors, Mediators, and Moderators. Spirituality (*Native American Spirituality Scale, Traditional Spiritual Activities scale*)

Standard measures:

Mental health/well-being (e.g., self-esteem, GAD-7, and PHQ-8) for youth and culturally-specific stressors such as familial historical trauma, microaggressions, in-community microaggressions.

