Journey of Transformation Curriculum for Native American Adolescents (JOT)

NCT05274217

[name]

Statistical Analysis Plan

IRB Approved 03-16-2021

Statistical Design and Power

This study will evaluate the following primary outcomes: (1) alcohol, tobacco, and other drugs (ATOD; intentions to use, overall use, susceptibility, refusal self-efficacy) and (2) sexual and reproductive health (sexual activity, sexual self-efficacy, safer sex intentions). An intent-to-treat approach will be used to estimate the magnitude and statistical significance of intervention effects at immediate post-intervention. Each outcome will be evaluated in a separate generalized linear mixed model to evaluate the effect of CHJOT curriculum on intervention outcomes. Continuous outcomes will be modeled using a Gaussian link function for normally distributed data and binary outcomes using a logit link for Bernoulli-distributed data. The following equation represents the basic model for the outcomes: $Outcome_{tij} = b_0 + b_1 Intervention_i + b_2 Time + b_3 (Intervention_{ij} \times Time_{tij}) + u_{0i} + r_{0ij} + e_{tij}$, where t indexes assessment, i indexes individual, and j indexes classroom. The last three terms on the right side of the model equation represent the variability between classrooms (u_{0i}), between individuals within classroom (r_{0ij}), and residual error (e_{tij}), respectively. The statistical test of the CHJOT curriculum will be the Intervention by Time interaction, which will evaluate whether recipients of the intervention curriculum improved more or decreased less from pre- to 2-month post-intervention compared with waitlist control.

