To estimate the necessary sample size for our Longitudinal Mediation Model. We assume 80% power to detect a small intervention effect of $d = 0.22$ (standardized mean effect) of CJT (immediate intervention) vs. Waitlist control in pre-intervention to 3 month post-intervention outcome change. We base our power analysis on a repeated measures ANOVA design evaluating the Intervention by Time interaction in the primary outcome analysis, assuming a Type I error rate of 5%. Assuming a moderate temporal stability ($r = .25$) of the outcome measures, which is reasonable given the short interval between assessments, post-baseline data from 255 participants will be necessary to detect an intervention effect equivalent to a Cohen's d as low as 0.20, which would accommodate a 10% reduction in the observed intervention effect due to potential early exposure of control participants to the intervention (i.e., contamination effects). We anticipate a modest attrition rate of 15%, as the intervention will be offered in a required class in a boarding school indicating an analytic sample of 216 participants. Thus, our planned recruitment of 255 participants will provide a sufficient sample to detect targeted intervention effect, after accounting for attrition.

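### The SAP's 80% power figure is worked out for a mean-difference ANOVA only; no power is given for yes/no primary outcomes, and at 216 analysed their logit test falls below 80% under any assumed prevalence from 10% to 50%

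*SAP*

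**What the plan says.** The SAP (Statistical Design and Power) names seven primary constructs. Four concern substance use: intentions, overall use, susceptibility and refusal self-efficacy. Three concern sexual health: activity, self-efficacy and safer sex intentions. Each gets its own generalized linear mixed model, with continuous outcomes treated as Gaussian and "binary outcomes using a logit link for Bernoulli-distributed data". The test is the Intervention by Time interaction.

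The second paragraph gives the only power calculation. It opens with "We assume 80% power to detect a small intervention effect of" d = 0.22, described as a standardized mean effect, and continues: "We base our power analysis on a repeated measures ANOVA design evaluating the Intervention by Time interaction in the primary outcome analysis". The other inputs are "assuming a Type I error rate of 5" percent, a correlation of .25 between assessments, and a sample said to be enough "to detect an intervention effect equivalent to a Cohen's d as low as 0.20" after allowing for contamination. Recruitment is 255, attrition 15% and the analytic sample 216. The paragraph concludes that the sample is sufficient.

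Protocol 5.4 describes the measures. On current alcohol use: "Participants will be asked if they drank alcohol in the past 30 days". Whether intercourse has occurred is one item among the sexual activity measures, which also cover frequencies and number of partners. Susceptibility, refusal efficacy and safer sex intentions are multi-item scales.

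**The concern.** A power figure for a difference in means does not carry over to a yes/no outcome. A binary response carries less information than a score, and progressively less as prevalence moves away from 50%. Neither document gives a prevalence, an odds ratio, a detectable difference or a power for any binary outcome, yet the single ANOVA figure is presented as covering the primary outcome analysis as a whole.

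Overuse of that figure would affect the behaviours themselves. Protocol 1.5 lists lower substance use and delayed sexual initiation among the intended outcomes. If a yes/no measure of either comes out non-significant, a reader holding the SAP could set that result against 80% power that was never calculated for it.

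**Working it through.** **Inputs from the SAP.** Type I error 5% (sidedness not stated; two-sided used here); d = 0.22, or 0.20 after contamination; r = .25; 255 x 0.85 = 216.75, hence 216 analysed.

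**Assumptions.** 1:1 allocation, so 108 per arm; prevalence p of 10-50%, equal in the arms at baseline and steady in controls; the programme lowers prevalence; within-student correlation .25 for the binary response; no classroom effect. The documents state none of these for a binary outcome.

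**Step 1: the SAP's own figure.** For a 2 x 2 repeated-measures interaction, the noncentrality is 2N f²/(1 − r), referred to F(1, N − 2). With f = d/2:

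- N = 216, d = 0.20: 2 x 216 x 0.0100/0.75 = 5.76, power 66.6%.
- N = 216, d = 0.22: 2 x 216 x 0.0121/0.75 = 6.97, power 74.8%.
- N = 255: 73.8% at d = 0.20 and 81.5% at d = 0.22.
- N for 80% power: 298 (d = 0.20) or 246 (d = 0.22); one-sided, 234 or 194.

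The SAP's pairing of 255 with d = 0.20 is not reproduced. The nearest match is 255 with d = 0.22. At 216, 80% is not reached even for a continuous outcome.

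**Step 2: what d means.** With unit SD, a between-arm difference in change of Δ gives f = Δ/4. So f = d/2 amounts to Δ = 2d, that is 0.40-0.44 SD (reading B). If d is instead the raw-SD difference in change, Δ = d and f = d/4 (reading A). The noncentrality at 216 is then 1.44 or 1.74, and the continuous test has 22.3% or 26.0% power.

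**Step 3: to the odds-ratio scale.** ln(OR) = −Δ x π/√3.

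- Reading A: OR 0.70 (Δ = 0.20) or 0.67 (Δ = 0.22).
- Reading B: OR 0.48 (Δ = 0.40) or 0.45 (Δ = 0.44).

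**Step 4: Wald test of the logit interaction.** With v = p(1 − p) and v₁ the same quantity at the intervention arm's post-test prevalence:

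Var = 2(1 − r)/(n v) + 1/(n v) + 1/(n v₁) − 2r/(n √(v v₁)).

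Example, p = 30%, Δ = 0.44: odds 0.4286 x 0.450 = 0.193, so the post-test prevalence is 16.2%. Var = 0.0661 + 0.0441 + 0.0683 − 0.0274 = 0.1511, SE 0.389. Then z = 0.798/0.389 = 2.05 and power = Φ(2.05 − 1.96), about 54%.

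| Prevalence | A, d = 0.20 | A, d = 0.22 | B, d = 0.20 | B, d = 0.22 |
|---|---|---|---|---|
| 10% | 9.6% | 10.5% | 21.8% | 24.9% |
| 20% | 13.4% | 15.2% | 36.3% | 41.7% |
| 30% | 16.4% | 18.8% | 46.9% | 53.7% |
| 50% | 19.2% | 22.2% | 57.1% | 65.0% |
| Continuous outcome | 22.3% | 26.0% | 66.6% | 74.8% |

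**Step 5: simulated mixed model.** A random-intercept logistic model (latent intraclass correlation .25, likelihood-ratio test, 400 runs per setting) gave 7.8%, 12.3% and 14.0% at prevalences of 10%, 30% and 50% for Δ = 0.22. For Δ = 0.44 it gave 22.3%, 33.8% and 44.8%. These are lower than the Wald values, as expected: here the odds ratio is within-student and implies a smaller shift in population prevalence.

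**Step 6: sensitivity.** With all 255 analysed (127.5 per arm), the best Wald case in the table (p = 50%, OR 0.45) rises to 72%. With r = .5 in place of the SAP's .25, reading B with d = 0.22 gives 34% at p = 10%, 71% at 30%, 78% at 40% and 82% at 50%. Reaching 80% therefore takes both a higher correlation than the SAP assumes and a prevalence near one half.

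**The case against.** The strongest reply is that the SAP describes its effect as a standardized mean effect, so a careful reader would apply the figure to scale scores only. Protocol 1.5 speaks of preliminary efficacy, and Protocol 1.8 presents the data as the basis for later, larger trials. That limits the consequence, but the SAP still ties its figure to the primary outcome analysis without excluding binary outcomes.

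Four stronger readings are tempting, and the documents do not support them.

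- A reader might set 80% against roughly 10-20% and blame the gap on the outcomes being yes/no. That mixes two readings of d. Where the logit test has 8-22%, the continuous test has only 22-26%, so most of that drop comes from how d is defined.
- A reader might infer that several primary outcomes are binary. The SAP labels none. From Protocol 5.4, at most two of the seven constructs look yes/no, and sexual activity also has index, frequency and count items.
- A reader might conclude that a non-significant behavioural result is nearly certain. At 22-65% power that does not follow, and the SAP nowhere says how such a result would be interpreted.
- A reader might size the shortfall from a post-test comparison of proportions. The SAP does not use that test.

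It is also fair that every binary figure here rests on assumed prevalences, and that the SAP's model has a classroom term which these calculations omit.

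**Conclusion.** The point holds as an unsupported power statement. The SAP gives power for a continuous outcome only, plans logit models for binary primary outcomes, and says nothing about their power. Under the assumptions listed, the logit interaction test at 216 is below 80% at every prevalence from 10% to 50%: about 8-22% if d is the raw-SD difference in change, and about 22-65% on the f = d/2 reading. The like-for-like loss from a yes/no outcome is the gap between those ranges and the continuous test's 22-26% and 67-75% respectively.

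The direction is secure at the SAP's own correlation. The exact values are not: they depend on the definition of d, the conversion to an odds ratio, the prevalence, and equal allocation. A classroom effect could lower power further if assignment follows classes. Settling whether 255 or 216 is the analysed number would not cure the problem, and simply confining the existing 80% to continuous scores would keep a figure that itself fails at 216.

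**What to change.** In the power paragraph of the SAP:

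1. Define d explicitly: difference in change in raw SD units, in change-score SD units, or the ANOVA effect with f = d/2.
2. State that the power figure applies only to continuous scale scores, and restate it for 216 analysed. On the f = d/2 reading that is about 67% at d = 0.20 and 75% at d = 0.22.
3. State which primary outcomes are analysed as binary. For each, give the power or the detectable odds ratio at 216 over a stated prevalence range.
4. If enough baseline surveys were completed, take prevalences from the discontinued wave, for which Protocol 4.4 says "we are paying enrolled participants for completing the baseline assessment". Those students did not go through the intervention, so their baseline data reveal no arm comparison. The protocol does not say how many surveys there are.
5. Report yes/no outcomes as estimates with confidence intervals, and state that non-significance is not evidence of no effect.

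The cost is one recalculation and some wording. Enrolment, design and tests stay as they are; the stated power becomes less favourable.

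### The SAP uses 255 both as the number needed with post-baseline data and as the number recruited before 15% attrition; the 216 left do not give 80% power on the stated two-wave test

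*SAP*

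**What the plan says.** The SAP's only sample-size justification is the last paragraph of Statistical Design and Power.

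- Target: "We assume 80% power to detect a small intervention effect of" d = 0.22, for immediate intervention against waitlist in "pre-intervention to 3 month post-intervention outcome change".
- Method: "We base our power analysis on a repeated measures ANOVA design evaluating the Intervention by Time interaction", with a 5% type I error rate and r = .25 between assessments.
- Required number: "post-baseline data from 255 participants will be necessary to detect an intervention effect" as small as d = 0.20. The lower d allows for a 10% loss of effect through contamination (0.22 x 0.9 = 0.198).
- Attrition: "We anticipate a modest attrition rate of 15" per cent, "indicating an analytic sample of 216 participants".
- Conclusion: "our planned recruitment of 255 participants will provide a sufficient sample to detect targeted intervention effect, after accounting for attrition".

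The analysis paragraph before it describes the test as whether intervention recipients "improved more or decreased less from pre- to 2-month post-intervention compared with waitlist control". The two paragraphs label the follow-up point differently (2 and 3 months), but both describe one pre-to-post contrast, which is two waves.

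The SAP does not give the SD behind d, the conversion from d to an ANOVA effect size, the sidedness, the allocation ratio or the number of waves used in the calculation.

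**The concern.** A participant lost before follow-up supplies no post-baseline data. A requirement for post-baseline data from 255 people is therefore a requirement on the number analysed, and it cannot also be the number enrolled before a 15% loss. The reader cannot tell which number the trial needs.

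A charitable reader would take 216 as the requirement and 255 as the inflated recruitment target. The question is then whether 216 gives 80% power for d = 0.20 to 0.22. If it does not, the chance of missing an effect of that size exceeds the 20% the SAP implies, and a null result could be read as stronger evidence of no effect than it is.

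**Working it through.** **Inputs from the SAP:** type I error 5%; power 80%; d = 0.22, and 0.20 after contamination; r = .25; attrition 15%; 255 and 216. Two waves follows from the pre-to-post contrast. **Assumptions:** two-sided test, 1:1 allocation, continuous outcome, no classroom clustering, no multiplicity adjustment.

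**1. Attrition**

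- 255 x 0.85 = 216.75, so 216 is 255 after attrition.
- 216/0.85 = 254.1, which rounds up to 255.
- 255/0.85 = 300, the recruitment needed if 255 must be analysed.

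**2. Trying to reproduce 255 with the stated method**

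For the Intervention by Time term with m = 2 waves and f = d/2, lambda = f² x N x m/(1 - r), referred to a noncentral F with 1 and N - 2 degrees of freedom.

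- N = 255, d = 0.20: lambda = 0.01 x 255 x 2/0.75 = 6.80; power 73.8%.
- N = 255, d = 0.22: lambda = 0.0121 x 255 x 2/0.75 = 8.23; power 81.5%.
- N for 80%: 298 at d = 0.20 and 246 at d = 0.22.

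So 255 analysed roughly fits d = 0.22, but not the d = 0.20 to which the SAP attaches it.

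**3. Power at 216, same method**

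- d = 0.20: lambda = 0.01 x 216 x 2/0.75 = 5.76; power 66.6%.
- d = 0.22: lambda = 0.0121 x 216 x 2/0.75 = 6.97; power 74.8%.

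**4. What f = d/2 implies**

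A t test on change scores has squared noncentrality (difference)² x N/(4 x 2(1 - r)). Setting this equal to lambda = d² x N/(2(1 - r)) gives a difference of 2d. The convention therefore credits the trial with a difference in change of 0.40 to 0.44 outcome SD. A t test with those differences returns the same 66.6% and 74.8%; simulation (40,000 runs) gave 66.3% and 74.7%.

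**5. Other meanings of d**

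Noncentral t, noncentrality = d/sqrt(4V/N). V is 2(1 - .25) = 1.5 if d is in outcome-SD units, 1 if in change-score SD units, and 1 - .25² = 0.9375 for ANCOVA (N - 3 degrees of freedom). ANCOVA is not the SAP's method and is shown for comparison only.

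| Reading (d = 0.20 / 0.22) | Power at 216 | Power at 255 | N analysed for 80% |
|---|---|---|---|
| Difference in change, outcome SD | 22% / 26% | 25% / 30% | 1,180 / 976 |
| Difference in change, change-score SD | 31% / 36% | 36% / 42% | 788 / 652 |
| ANCOVA | 33% / 38% | 38% / 44% | 738 / 612 |
| Repeated measures ANOVA, f = d/2 | 67% / 75% | 74% / 82% | 298 / 246 |

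**6. What would bring 216 up to 80%** (ANOVA with f = d/2, d = 0.20 / 0.22)

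- A higher r: about .455 / .34 instead of .25.
- A one-sided test: 77% / 84%.
- Three waves: 75% / 83%.
- Four waves: 82% / 89%.

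**7. Detectable effect at 216** (two waves, two-sided, 80% power): 0.469 outcome SD in change, equal to 0.383 change-score SD, or d = 0.235 if f = d/2.

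**The case against.** The strongest reply is that this is a slip in one clause. The last two sentences of the paragraph agree with each other, since 216 inflated for 15% attrition is 255, and only the clause on post-baseline data conflicts. That is plausible, but it does not rescue the claim, because 216 falls short on the SAP's own test. The opposite slip is also plausible: 255 analysed gives 81.5% for d = 0.22.

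A second reply is that the spread from 22% to 75% mixes methods. In part that stands. The SAP names one method, and on it the best case is 67%/75%, a modest miss at d = 0.22. ANCOVA should not count against the plan. The change-score readings are fair, because the SAP describes d as a standardised effect on outcome change. The spread reflects an undefined d; it is not an estimate of the trial's true power.

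Third, some calculations do pass at 216. A one-sided test passes at d = 0.22 only, as do three waves; four waves pass at both values. No one-sided test is stated. Extra waves do not match the pre-to-post contrast, and waitlist students start the intervention in the spring (protocol 5.1), so later assessments are not an untreated comparison. Entering d itself as f also passes (83%/89% under one software option), but that would be an input error.

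Finally, protocol 2.8 lists up to 450 students. That is a ceiling on completers, which the SAP does not use, so it does not settle which N is required.

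**Conclusion.** The concern holds. The contradiction is in the text and needs no model: 255 cannot be both the required number with post-baseline data and the number recruited before a 15% loss.

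Separately, 80% power for d = 0.20 to 0.22 is not reached at 216 on any two-wave, two-sided reading tried. On the stated ANOVA with f = d/2 it is 67% to 75%; on the change-score readings it is 22% to 36%. The chance of missing such an effect is therefore about 25% at best (1 - 0.748) and about 78% at worst (1 - 0.223), depending on what d means, against the stated 20%.

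These figures rest on r = .25, 1:1 allocation and a continuous outcome. They leave out the classroom term in the SAP's own model and any adjustment across its several primary outcomes; positive clustering or such an adjustment would generally lower power further. Binary outcomes were not examined.

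**What to change.** Amend the sample-size paragraph of the SAP:

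1. State whether 255 or 216 is the required number with post-baseline data, and correct the other sentence.
2. State the definitions used when the number was derived: the SD behind d, the conversion from d to the ANOVA effect size, sidedness, allocation ratio and number of waves. Record these before any alternative is considered, so that the test is not chosen to recover the 80%.
3. Withdraw the claim of 80% power for d = 0.20 to 0.22 at 216 analysed, and restate power and the detectable effect on the declared definition. With two waves, a two-sided 5% test, r = .25, 1:1 allocation and 216 analysed, the detectable difference in change is about 0.47 outcome SD (0.38 change-score SD), or d = 0.235 if f = d/2. Label it as applying to continuous outcomes, with no clustering and no multiplicity adjustment.
4. If a one-sided test or more waves was intended, say so and give the power on that basis.

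The cost is wording only, with no added participants and no change of analysis. The stated power or detectable effect becomes less favourable.
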